Safety of Direct Acting Antiviral Medications for Patients with Hepatitis C

NCT03423641

1/31/2018

Statistical Analysis Plan

Overview

We will use two different analytic approaches to answer the question of interest: a Poisson regression model and marginal structural modeling (MSM). These are described in more detail below. The simpler Poisson model is an extension of tabular rate of event analysis. The more complicated MSM model incorporates modeling of the treatment decision to more flexibly control for confounding by indication. For each outcome, we will only record the first date an outcome occurs. Also, each outcome will be modeled separately.

Detailed Description of Methods

Descriptive Statistics. We will calculate descriptive statistics at study entry. We will test for differences between the study sites using ANOVA, Chi-Square tests, and t-tests as appropriate. Similarly, we will test for differences between those who receive treatment and those who do not.

Poisson Regression Model. We have selected a Poisson regression approach to estimate case-mix adjusted outcome rates. This facilitates comparison to simpler tabular analyses. People may contribute multiple observations to the data set as covariates change over time.

Model:

$Y_{ij} \sim \text{Pois}(\lambda_{ij} T_{ij})$ Where Y_{ij} is assumed to be either 1 or 0 depending on whether the current outcome of interest occurred during the j^{th} exposure window of the i^{th} person, λ_{ij} is the expected daily rate of events for the the j^{th} exposure window of the i^{th} person and T_{ij} is the length of the j^{th} exposure window for the i^{th} person.

The j^{th} exposure window ends when one of the following occurs: end of study, end of membership, death, initial DAA Rx dispensed, a covariate changes (only if $\text{Trt}_{ij} = 0$), post-DAA follow-up time reached (only if $\text{Trt}_{ij} = 1$) 30, 90, or 180 days from the initial DAA prescription dispense, or current outcome of interest occurs.

As is common for a Poisson regression model, we let

$\log(\lambda_{ij}) = \beta_0 + \beta_1 \text{Trt}_{ij} + \vec{X}_{ij} \vec{\beta}$ where Trt_{ij} indicates whether the i^{th} individual transitioned to DAA at the start of their j^{th} exposure window. Once the initial prescription for DAA is dispensed, they transition from $\text{Trt}_{i(j-1)} = 0$ to $\text{Trt}_{ij} = 1$ for the remainder of the study. After the transition, to prevent mediation, no covariates are updated. \vec{X}_{ij} is the vector of covariates for the the j^{th} exposure window of the i^{th} person.

The main parameter of interest, once exponentiated as $e^{\beta_1} = \text{IRR}$, can be interpreted as the ratio of the rate of an individual adverse event for people taking DAA compared to those who do not, after adjusting for possible confounders \vec{X}_{ij} .

Alternatively, we allow multiple treatment groups to be defined based on the total days supply of DAA received during the study.

Marginal Structural Modeling (MSM) can be thought of as the extension of propensity score weighting to treatment decisions over time. In propensity score modeling, the comparison and treatment arms are weighted to match the treatment of interest on baseline covariates. MSM extends this idea to modeling repeated opportunities to initiate treatment over time.

Following the notation of Robins et al. 2000, let V_i denote the vector of baseline static covariates, let L_{ik} denote the vector of time-varying covariates, and let A_{ik} denote the treatment group, and Y_{ik} denote the outcome for person i at time k .

We will fit the pooled logistic regression model for each outcome

$$\text{logit}(P_{ik}) = \beta_0 + \beta_1 a_{ik} + \vec{\beta}_V V_i$$

where $P_{ik} = P(Y_{ik} = 1)$ and each observation Y_{ik} will be weighted using the inverse probability of treatment weight (IPTW)

$$W_{ik} = \prod_{t=0}^k \frac{1}{P(A_{it} = a_{it} \mid a_{i(t-1)}, L_{it}, V_i)}$$

Note that at each point of time we are weighting by the inverse of the probability of the treatment received rather than the probability of receiving DAA. While treatments can vary over time, once an individual receives DAA, they are in the DAA treatment group for the remainder of the study, so

$$P(A_{ik} = 1 \mid a_{i(k-1)} = 1, L_{ik}, V_i) = 1.$$

Weighting each observation using IPTW effectively creates a pseudo-population of subjects in which treatment is no longer confounded by V or L , thus $\hat{\beta}_1$ is an unbiased estimator of the the causal effect of treatment, if there is no unmeasured confounding.

For each time period k , we will fit the following logistic regression for the treatment conditional on all observed covariates.

$$\text{logit}(P(A_{ik} = 1 \mid A_{i(k-1)}, L_{ik}, V_i)) = \gamma_{0k} + \vec{\gamma}_L L_{ik} + \vec{\gamma}_V V_i.$$

Additional steps will be explored, such as cubic splines, to smooth β_{0k} over time. Also, since W_{ik} tend to be highly variable with small probabilities in the denominator leading to large weights, we will explore using the stabilized weight

$$SW_{ik} = \prod_{t=0}^k \frac{P(A_{it} = a_{it} \mid a_{i(t-1)}, V_i)}{P(A_{it} = a_{it} \mid a_{i(t-1)}, L_{it}, V_i)}$$

Note that the numerator only depends on covariate values at baseline since it does not depend on L_{it} . The stabilized weight preserves unbiased estimation of the causal effects

of treatment while maintaining the same effective sample size as the original dataset. If some weights are still extreme, we will truncate the weights.

Similar to the treatment model, we will fit a logistic regression to model the probability of being censored. In order to obtain an unbiased estimate of the causal effect of treatment after accounting for both censoring and confounding, we will let each time period k in the outcome model be weighted by the combined weight

$$SW_{ik} \times SW_{ik}^+$$

where

$$SW_{ik}^+ = \prod_{t=0}^k \frac{P(C_{it} = c_{it} \mid a_{i(t-1)}, V_i)}{P(C_{it} = c_{it} \mid a_{i(t-1)}, L_{it}, V_i)}$$

We will perform diagnostics on the weights to determine if the weights satisfy the assumptions necessary for performing MSM. Violations will result in adjusting the treatment and censoring models as needed until the weights are able to satisfy the assumptions and account for observed confounding.

Although no observational study can claim to be free from confounding, the preliminary results from KPSC demonstrate that we can identify and account for the differences between groups in the methods that we are using. It is worth noting that at this point a randomized trial (the only sure way to avoid confounding) would be unethical. Further, this is a study of the safety of these agents so we anticipate finding either that there are safety problems or that there are not safety problems and either result, with an adequately powered study, will be useful to patients and their physicians who are making decisions about this treatment.

Missing data

At the KP sites the EHR is relatively mature. Based on our experience in the pilot study, we do not anticipate much missing data for typical data elements like treatments, demographics, vital signs, and lab values. We will run usual checks on variables to identify the rate of missing data for key variables and will identify variables with more than 5% of missing data. The OneFlorida sites carefully monitor the fields that are submitted with valid data. OneFlorida partners were asked to submit enhanced laboratory data with elements that are not included in the PCORnet Common Data Model. These enhanced laboratory data are necessary for the HCV study and others. UFHealth, Health Choice Network, Florida Hospital, and Tallahassee Memorial Hospital, which comprise the major providers within OneFlorida. We do not anticipate much missing data.

For most EHR based data elements we anticipate very low levels of missing data, typically less than 1%. For example, missing rates in the KPSC Hep C populations are: eGFR – 1.0%, Gender – 0.1%, Age – 0.1%, Race – 4.0%. Race imputation will be performed using the BISG algorithm from RAND. These values are already routinely calculated in the KP system. Other values will be imputed with mean value substitution. Sensitivity analysis will be performed by comparing to complete case analysis. Should

there be evidence that this missing data is influential full multiple imputation will be employed. Perhaps not best thought of as missing data there are variables that may be drivers of the treatment decision that may not have been collected. Potentially the most important of these is the MELD score of liver function with a missing rate of nearly 10%. The decision to collect the elements of the MELD score is likely a function of health status. It may be necessary to treat the decision to generate a MELD score as an endogenous process and use structural equation models to understand the effects of MELD scores on the treatment decision.

If more than trivial amounts of missing data occur, we will use multiple imputation and the corresponding analysis procedures to incorporate the estimated effects of imputation on coefficients and their standard errors. Disenrollment can be handled directly in the MSM model with an incorporated model for censoring.

Dropout will result primarily from a lapse in membership or death. Membership and death records are kept by the insurer and will be used to record and report dropout. As this is a retrospective analysis of data collected during patient care and stored in the EHR, reasons for missing labs and demographics will be unknown and not reported.

A complete case analysis will be compared to imputation based analysis.

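### The days-supply groups in the alternative Poisson analysis are defined by dispensing after the treated clock starts, so their rate ratios are biased for outcomes that can end dispensing

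*SAP*

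**What the plan says.** All of this is in the SAP, under Poisson Regression Model.

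- **Main exposure.** The indicator Trt "indicates whether the i^{th} individual transitioned to DAA at the start of their j^{th} exposure window". It switches from 0 to 1 at the first dispense and stays at 1.
- **Clock.** Treated time ends at "30, 90, or 180 days from the initial DAA prescription dispense, or current outcome of interest occurs", or at one of the general endings. Among dispensings, only the first ends a window: "end of study, end of membership, death, initial DAA Rx dispensed".
- **Updating.** "After the transition, to prevent mediation, no covariates are updated".
- **Alternative exposure.** "Alternatively, we allow multiple treatment groups to be defined based on the total days supply of DAA received during the study".

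No other time origin, landmark, lag or time-varying definition is given for the supply groups. Under Overview, each outcome is modelled separately and only its first date is recorded.

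**The concern.** Total supply over the whole study is not known when the treated window opens. It is settled by later fills and, for the 30-day window, by fills made after the window has closed. Two errors follow when an outcome sometimes ends dispensing:

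- **Reverse causation.** The event cuts the course short, so the patient is counted in a low-supply group because of the event.
- **Immortal time.** To reach a high-supply group a patient must keep collecting fills. The early time in that group's denominator could therefore not contain an event that ended dispensing.

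Adjusting for covariates cannot repair this, because the group label is partly a consequence of the outcome. Short courses will tend to look harmful and full courses protective even if DAA has no effect. In a safety study that pattern could be read as a dose or duration signal.

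**Working it through.** The SAP gives no event rate, fill pattern or outcome list, so it has no figure to reproduce. The size has to come from stated assumptions.

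**Inputs from the SAP:** treated time starts at the first dispense; horizon H = 30, 90 or 180 days; group fixed by total supply over the study.

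**Assumptions not in the SAP:** fills on days 0, 28 and 56 (84 days in all); event rate 5% per year, constant; 5% unrelated stopping at each refill; true rate ratio 1.00. The share of events that end dispensing is q, and the share of patients on a planned 56-day course is p. Both are unknown, so both are varied.

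**Formula.** Let s be the proportion short of full supply for reasons unrelated to the event: s = 1 − (1 − p) × 0.95². With p = 0, s = 1 − 0.9025 = 0.0975. An event before day 56 leaves the patient in the full-supply group with probability (1 − s)(1 − q); an event on or after day 56 does so with probability 1 − s. Ignoring the small loss of person-time after events, for H ≥ 56:

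- Full-supply ratio ≈ [56(1 − q) + (H − 56)] / H
- Short-supply ratio ≈ [56(s + (1 − s)q) + (H − 56)s] / (H s)

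For H = 30 the full-supply ratio is about 1 − q.

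**Example, q = 1, p = 0, H = 90.** Full: 34/90 = 0.38. Short: (56 + 34 × 0.0975)/(90 × 0.0975) = 59.3/8.78 = 6.8. Integrating exponential event times exactly gives 0.38 and 6.6.

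**Exact results (true ratio 1.00):**

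| q | Full supply, 30/90/180 days | Short supply, 90/180 days, p = 0 | p = 0.2 | p = 0.4 |
|---|---|---|---|---|
| 1 | 0.00 / 0.38 / 0.69 | 6.6 / 3.9 | 2.6 / 1.8 | 1.7 / 1.4 |
| 0.5 | 0.50 / 0.69 / 0.84 | 3.8 / 2.4 | 1.8 / 1.4 | 1.4 / 1.2 |
| 0.25 | 0.75 / 0.84 / 0.92 | 2.4 / 1.7 | 1.4 / 1.2 | 1.2 / 1.1 |
| 0 | 1.00 / 1.00 / 1.00 | 1.0 / 1.0 | 1.0 / 1.0 | 1.0 / 1.0 |

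The any-DAA ratio is 1.00 in every row. Simulation of 8 million people per scenario agreed within Monte Carlo error.

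**Sensitivity.**

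- Event rate: 2% to 10% per year moves the q = 1, 90-day, p = 0 short-supply ratio only from 6.7 to 6.5.
- Unrelated stopping matters much more for the short-supply group. A separate simulation (4 million treated patients per scenario, stopping 2.5% or 10% per refill, event rate 2% or 10% per year, p = 0) gave 90-day short-supply ratios of 3.60–12.61 (q = 1), 2.30–7.02 (q = 0.5) and 1.65–3.97 (q = 0.25).
- The full-supply ratios in that simulation hardly moved: 0.38–0.39, 0.68–0.70 and 0.84–0.85.

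**Test of the remedy.** With a constant hazard, assigning person-time to the supply dispensed so far gave ratios of 0.99–1.01 after fills 1, 2 and 3 for the 90- and 180-day windows, including q = 1. If background risk is doubled in the first 28 days with no supply effect (q = 1, p = 0, 90 days), the same analysis without a time term gives 1.90, 1.00 and 1.00. Time since dispense therefore has to be accounted for. Under doubled early risk with q = 1 or 0.5, comparing supply levels within time since dispense gave ratios of 0.94–1.02 after day 28, equal within Monte Carlo error.

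**The case against.** The alternative analysis is one permissive sentence with no categories, reference group or clock of its own. The window list and the no-update rule were written for the binary indicator, and the latter concerns covariates, whereas supply is the exposure. On that view the plan is under-specified, and biased only if followed literally. Part of this stands: the first-dispense clock is carried over because it is the only one given. But total supply over the study is a whole-study quantity, and no later fill opens a new window, so a programmer following the text would build the biased groups.

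The size also depends on facts the SAP does not give. The short-supply ratios in particular should be read with the stopping-rate range, not as a single figure. The full-supply ratios and the direction do not share that weakness. The calculation uses only two supply groups, whereas the SAP allows several.

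The remedy has limits. With p = 0, everyone has the same supply up to day 28, so that period says nothing about supply. After it, the lower-supply side has only about 0.05 × 28 + 0.0975 × 34 = 4.7 of 90 person-days per patient, about 5%. Those are the patients whose stopping may be driven by health. The remedy also changes the question from total course received to exposure so far.

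Finally, this is not the main analysis. That limits the severity but does not make the groups valid.

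**Conclusion.** The concern holds. As written, the supply-group analysis classifies patients by dispensing that follows the start of follow-up and that the outcome can cut short. Under the assumed fills and no drug effect, the 90-day full-supply ratio falls to 0.38–0.84 as q goes from 1 to 0.25. The short-supply ratio rises above 1 in every scenario with q above 0; at 90 days it runs from 1.2 (q = 0.25, p = 0.4) to 12.61 (q = 1, p = 0, 2.5% stopping). The direction is certain whenever some events end sequential dispensing; the size is not, because q, the fill pattern and the stopping rate are assumed. There is no bias at q = 0 or if the whole course is dispensed at once. The main any-DAA rate ratio and the marginal structural model, as written, are untouched. It should be fixed before the supply-group results are produced.

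**What to change.** In the SAP, Poisson Regression Model:

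1. Replace the alternative-groups sentence with: *Alternatively, we will define treatment groups by the cumulative days supply of DAA dispensed up to the start of each exposure window.*
2. Add *a further DAA dispense* to the events that end a window. Supply is the exposure, so the other covariates can stay frozen after the transition.
3. Compare supply categories with time since first dispense in the model, and state how that term is coded for untreated time, where it is undefined.
4. State that health-driven stopping can still confound these groups and may need weighting.
5. Report supply groups for the 90- and 180-day windows only. Under the assumed fills, just 2 days of the 30-day window follow the second fill (30 − 28).

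Grouping by intended course length is an alternative only if that is recorded at initiation. A landmark after supply is complete suits only the 180-day window: at day 56 it leaves 0, at most 34 and at most 124 days of the three windows. Labelling the present analysis descriptive would be cheaper but would leave the bias in the reported ratios.

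**Cost.** The wording changes are short and the programming modest, since total supply already has to be built from dispensing records. The price is less person-time per category, an extra model term, possibly a stopping model for weights, and a narrower question.

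### The printed MSM outcome model has no term for time and no post-DAA horizon, so its single treatment coefficient can absorb hazard trends, dilute a short-lived harm and differ from the Poisson result for reasons other than confounding

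*SAP*

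**What the plan says.** The Overview presents the Poisson model and the MSM as answers to one question: "We will use two different analytic approaches to answer the question of interest".

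- **Poisson Regression Model.** A treated exposure window closes at "30, 90, or 180 days from the initial DAA prescription dispense". The same section says treatment status stays at 1 "for the remainder of the study. After the transition, to prevent mediation, no covariates are updated".
- **Marginal Structural Modeling, outcome model.** It is introduced by "We will fit the pooled logistic regression model for each outcome" and printed as logit(P_ik) = β0 + β1·a_ik + β_V·V_i, where V_i holds only static baseline covariates. Treatment is absorbing: "once an individual receives DAA, they are in the DAA treatment group for the remainder of the study". No post-DAA limit is given for this analysis.
- **MSM, treatment model.** This one does have a period-specific intercept, γ0k. The next sentence begins "Additional steps will be explored, such as cubic splines, to smooth" and names β0k, a symbol found in none of the printed models.
- **MSM, claim for the estimate.** The estimated β1 "is an unbiased estimator of the the causal effect of treatment, if there is no unmeasured confounding".

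**The concern.** Two separate problems follow if the outcome model is fitted as printed and treated people are followed to the end of the study.

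1. **Dilution.** One β1 averages over all time after first dispensing. A harm limited to the early weeks is averaged with later time in which there is none. The Poisson and MSM estimates can then disagree with no confounding at all. Because the MSM is presented as the more flexible control of confounding, an MSM estimate near 1 beside a raised Poisson rate ratio could be read as confounding removed.
2. **Trend bias.** Since DAA status is absorbing, treated person-time falls later in the study than untreated person-time. The weights balance covariates within each period but do not make treatment independent of k. A rising or falling baseline hazard therefore enters β1. The stated condition for unbiasedness, no unmeasured confounding, is not enough. The printed model also needs a flat baseline hazard, or treated and untreated time spread alike over the study. The SAP's planned diagnostics lead only to changes in the treatment and censoring models, so they would not repair this.

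**Working it through.** The SAP gives no event rates, initiation rates or follow-up length, so there is no figure of its own to reproduce. Only the model forms and the 30/90/180-day limits below come from the SAP; every other input is an assumption.

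**Step 1. Where could time enter the outcome model?** β0 has no k subscript. V_i is static. a_ik records only whether DAA has started. So neither k nor time since dispensing is represented. β0k could be an outcome intercept whose subscript was left off the printed equation, or a slip for γ0k, which stands just before it.

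**Step 2. Dilution by simple averaging.** Assume a true ratio of 2.0 for d = 90 days, then 1.0, with flat baseline hazard. Over treated follow-up T the average ratio is (2d + (T − d))/T, with d capped at T.

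| T | Calculation | Ratio |
|---|---|---|
| 30 days (Poisson) | 60/30 | 2.00 |
| 90 days (Poisson) | 180/90 | 2.00 |
| 180 days (Poisson) | (180 + 90)/180 | 1.50 |
| 1 year | (180 + 275)/365 | 1.25 |
| 2 years | (180 + 640)/730 | 1.12 |
| 3 years | (180 + 1005)/1095 | 1.08 |

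If the harm is constant, every row is 2.00.

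**Step 3. Does a term for k cure dilution?** Expected-count pooled logistic fits used monthly periods, baseline risk 0.2% per month, 3% per month initiation and no confounding by L (so stabilized weights equal 1). The ratio was 2.0 for 3 months and then 1.0. With an intercept for every period, the odds ratio was:

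| Follow-up | Stabilized weights | Printed W_ik |
|---|---|---|
| 36 months | 1.18 | 1.26 |
| 60 months | 1.13 | 1.18 |

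So dilution remains even if β0k was meant as a period-specific outcome intercept.

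**Step 4. Trend bias under no effect.** Same set-up, true odds ratio 1, no time term, no horizon.

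| Setting | Hazard +10%/year | Hazard −10%/year |
|---|---|---|
| 60 months, 3%/month, stabilized | 1.13 | 0.87 |
| 60 months, 3%/month, W_ik | 1.08 | 0.91 |
| 36–60 months, 1–5%/month, stabilized | 1.05–1.17 | 0.85–0.94 |
| 36–60 months, 1–5%/month, W_ik | 1.05–1.08 | 0.91–0.95 |

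For a 5% yearly trend the stabilized ranges are 1.03–1.08 and 0.92–0.97. With a flat hazard, or with a quadratic in k added, the odds ratio is 1.00.

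**Step 5. Does a horizon cure the trend?** Treated follow-up was cut at 6 months, with 60 months, ±10% per year and stabilized weights. Constant 3% initiation gives 1.02/0.98. Initiation rising from 1% to 5% per month at mid-study gives 1.10/0.90.

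Each repair therefore deals with only one of the two problems. A separate calculation with 0.5% monthly risk agreed. A true ratio of 2.0 for 3 months became 1.41–1.43, 1.21–1.24 and 1.14–1.16 at 12, 24 and 36 months. A null effect gave 0.85–0.88 when risk halved over 24–36 months and 1.12–1.17 when it doubled.

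**The case against.** The strongest reply is that β is used for outcome models and γ for the treatment model. Smoothing β0k would then presuppose an outcome intercept that varies with k, and the printed equation merely lacks a subscript. On that reading the trend bias disappears. This is a fair reading, but the symbol directly follows the treatment model, so a slip for γ0k is as plausible, and the SAP does not settle it. Dilution survives either way (Step 3).

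Other points, and what stands of them:

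- **The SAP does not say the MSM runs to study end.** True. The Poisson section uses the same remainder-of-study wording beside its 30/90/180-day stop, so the phrase cannot decide it. The bias figures are conditional on that reading; the silence is itself what needs correcting.
- **The Poisson model has no explicit time term either.** This stands. The contents of its covariate vector are not specified, and Step 5 with rising initiation resembles its 180-day design. Adding time to the MSM alone could leave a difference between the two analyses.
- **The trend range is narrower with W_ik.** This stands, and both ranges are shown above. The SAP's combined weight uses the stabilized form.
- **An ever-treated effect is a legitimate estimand, and the Poisson windows still examine short-lived harm.** Both are true and limit the damage. But the MSM effect is not labelled as ever-treated, and the Overview presents both analyses as answering one question.

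**Conclusion.** The concern holds. As printed, the MSM outcome model cannot represent time, its horizon is unstated, and the unbiasedness claim needs more than the condition given. Under the assumed rates, a doubling confined to 90 days shrinks to about 1.25–1.08 over one to three years of treated follow-up. A null effect is displaced to 1.05–1.17 or 0.85–0.94 by a 10% yearly hazard trend with stabilized weights, and to 1.05–1.08 or 0.91–0.95 with W_ik.

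These sizes are illustrations, because the SAP supplies no rates. They vanish if harm is constant and baseline hazard flat, and the trend part vanishes if k is in the model. Confidence is high on the text and on the direction of the problem, lower on its size. It should be fixed before analysis but does not undermine the Poisson horizon analyses.

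**What to change.** 1. **Put time in the MSM outcome model.** Require a smooth function of k (for example a restricted cubic spline) or period intercepts, print the equation with it, and say whether β0k is the outcome intercept or a slip for γ0k. State also whether the Poisson covariates include calendar or study time, so that the two analyses treat time alike.
2. **State the MSM horizon.** Either apply the SAP's own 30/90/180-day horizons, or replace a_ik by time-since-dispensing bands such as 0–30, 31–90, 91–180 and over 180 days. Keep any ever-treated effect as a separately labelled estimand.
3. **Tidy the Poisson wording.** Reconcile the remainder-of-study sentence with the 30/90/180-day stop, for example by saying that Trt = 1 until the post-DAA follow-up time is reached. This is a clarification only.
4. **Qualify the unbiasedness statement** so that it also requires a correctly specified outcome model, including its dependence on time.

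The cost is some SAP wording and a few extra model terms. The drawback is that each band has a wider interval than one pooled effect.

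### With V in both numerators, the combined weight removes only confounding and selection by L given V; control of V rests on the outcome model's V terms, a condition the SAP does not state and its repair rule does not address

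*SAP*

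**What the plan says.** All of this is in the SAP, Detailed Description of Methods, under Marginal Structural Modeling (MSM).

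- Outcome model: "We will fit the pooled logistic regression model for each outcome", with an intercept, a treatment term and β_V V_i. V is introduced to "denote the vector of baseline static covariates"; its coding is not given.
- After defining W, whose numerator is 1: "Weighting each observation using IPTW effectively creates a pseudo-population of subjects in which treatment is no longer confounded by V or L". The one condition attached to unbiasedness is that there is no unmeasured confounding.
- Stabilized weight SW, introduced as something to explore: its numerator is P(A_it = a_it | a_i(t-1), V_i). The SAP remarks "Note that the numerator only depends on covariate values at baseline since it does not depend on" L. It then states "The stabilized weight preserves unbiased estimation of the causal effects".
- Combined weight: each time period is to "in the outcome model be weighted by the combined weight" SW × SW+. The numerator of SW+ also conditions on V.
- Diagnostics are carried out on the weights. Violations lead to "adjusting the treatment and censoring models as needed until the weights are able to satisfy the assumptions and account for observed confounding".

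**The concern.** Read in order, the text carries a property of W over to SW. W balances both V and L. SW balances L within levels of V and leaves the dependence of treatment on V in place. The move from W to SW therefore adds a condition for an unbiased β_1: the outcome model must have the right form in V. A reader of the SAP would think that the absence of unmeasured confounding is enough.

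The repair rule has the same gap. With the printed numerators, no improvement of the denominator models can make the weights account for confounding by V, and the model that does that work is not among those the rule names. If a baseline covariate acts in a curved way on both DAA start and an adverse event, and its term in the outcome model is too rigid, β_1 keeps residual confounding while the weights look sound. In a safety study a wrong answer in either direction matters.

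**Working it through.** The SAP gives no figure on this point, so there is nothing to reproduce. The check is algebra first, then simulation.

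**Algebra.** For a patient not yet on DAA, let f(a | past a, L, V) be the true probability of the observed treatment in one period. Weighting multiplies it by that period's factor:

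- W: f(a | past a, L, V) × 1 / f(a | past a, L, V) = 1, which depends on neither V nor L.
- SW: f(a | past a, L, V) × f(a | past a, V) / f(a | past a, L, V) = f(a | past a, V), which is free of L but still depends on V.
- V-free numerator: f(a | past a, L, V) × f(a | past a) / f(a | past a, L, V) = f(a | past a), which is free of both.

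The same steps with C in place of A show that SW+ leaves censoring dependent on V.

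**Simulation 1 (all strengths assumed).** 40 replicates of 30,000 patients over 8 periods. V is standard normal, L is binary and time-varying, treatment is irreversible, there is no censoring and the true log odds ratio is 0. Start logit = −2.8 + 0.7L + 0.5s; event logit = −5 + 0.7L + 0.5s. Here s = V (linear case) or s = (V² − 1)/√2 (quadratic case). The treatment models include V and V². Entries are mean log odds ratios (Monte Carlo SE).

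| Analysis | V acts linearly | V acts quadratically |
|---|---|---|
| Crude | 0.389 (0.007) | 0.612 (0.008) |
| W, linear V | 0.002 (0.008) | −0.023 (0.014) |
| W, linear V, time | 0.004 (0.008) | 0.003 (0.015) |
| SW, no V | 0.321 (0.007) | 0.556 (0.008) |
| SW, linear V | 0.005 (0.007) | 0.556 (0.008) |
| SW, V + V² | 0.005 (0.007) | 0.001 (0.010) |

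The treated-minus-untreated difference in s (SD 1) was 0.000 and 0.002 after W, and 0.595 and 0.622 after SW. Mean SW was 1.000 and its effective sample 97.4% and 97.6% of rows, so the usual summaries of the weights look good in both cases. For W the effective sample was 31.6% and 32.2%.

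SW without V leaves 0.321 even in the linear case, so the weights are not removing confounding by V; the V term is. In the quadratic case the linear term fails: exp(0.556) = 1.74 against a true 1.00.

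**Simulation 2 (milder curvature, assumed).** 60,000 patients, V clipped at ±2.5, no drug effect. Start logit = −4 + f1·V + f2·V² + 0.5L; event logit = −7 + 0.6V + g2·V² + 0.5L. The first two rows use 24 months and 7 replicates, the last two 36 months and 4 replicates with f1 = 0.5.

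| f2, g2 | OR, SW linear V | OR, SW V + V² | Log difference |
|---|---|---|---|
| −0.25, 0.15 | 0.979 | 1.021 | −0.043 (SE 0.004) |
| −0.5, 0.25 | 0.919 | 1.023 | −0.107 (SE 0.005) |
| 0, 0.25 | 0.999 | 0.979 | ln(0.999/0.979) = +0.020 |
| 0, 0 | 1.011 | 1.012 | about 0 |

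V-free numerators gave 1.020 and 1.024 in the first two rows, matching the quadratic fit. The paired difference is the informative column: in repeat runs of a similar design each single log odds ratio had an SE of 0.01 to 0.02. Those repeats gave differences of −0.049, −0.133 and +0.027, and further runs gave −0.05 to −0.12 or +0.05.

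**The case against.** The strongest reply is that this is the textbook stabilized MSM. V in the numerator is legitimate because V is in the outcome model, and the SAP prints it there. The linear case above (0.005) bears this out. The pseudo-population sentence precedes SW and is true of W, and W is itself defined as a weight for the outcome model. All of this stands, and it is why the point is not an error of method.

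The reply also disposes of several stronger readings that a reader might infer:

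- That V enters as a single linear term that nobody checks. V is a vector whose coding is not given, so it may hold categories or transformed terms, and silence about a check does not show there will be none.
- That analysts would re-specify correct treatment models without end. This needs a marginal balance check of V, and the SAP names none. Nor does the repair rule bar a change to the numerator or outcome model.
- That V imbalance after SW is bias. It is expected by design. In simulation 2, with f2 = 0 and g2 = 0.25, the weighted standardized difference in V at month 24 was 0.77, yet the linear-V odds ratio was 0.999.
- That the bias runs toward no harm. Its sign changes with the assumed curvature: upward in simulation 1, mostly downward in simulation 2.

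What the reply does not meet is the text itself. The condition that SW adds is not stated, and a rule that revises treatment and censoring models until the weights account for observed confounding sets a target for V that the printed weights cannot reach.

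**Conclusion.** The point holds as a vulnerability to misspecification. With SW × SW+ as printed, an unbiased β_1 requires a correct form for V in the outcome model as well as correct weight models and no unmeasured confounding. The algebra for this needs no assumed strengths. The size does: shifts on the log scale ran from about −0.13 to +0.05 under moderate curvature, were nil when V acted linearly on both start and outcome, and reached 0.556 in a deliberately strong, purely quadratic case. None of these figures estimates the bias in this cohort, whose size and direction are unknown. The change is a cheap improvement, not a correction of an invalid analysis.

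**What to change.** 1. In the pooled logistic outcome model, enter the continuous elements of V with pre-specified flexible terms, for example restricted cubic splines, and list the outcome model's V terms among the items the diagnostics may revise.
2. For each outcome add a sensitivity fit with V removed from both numerators, P(A_it = a_it | a_i(t-1)) and P(C_it = c_it | a_i(t-1)), with time terms. Assess weighted balance of V there, where it is attainable. This fit relies on the denominators being right in V, which the weight diagnostics can examine.
3. Reword the claim, for example: SW and SW+ remove confounding and selection by L given V; confounding by V is handled by the outcome model and requires its V terms to be correctly specified.

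The cost is a few degrees of freedom, somewhat more variable weights in the sensitivity fit, and one extra fit per outcome. No new data are needed.
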